7.2. Safety endpoints

Primary safety endpoint is **mortality rates at 30 days** after surgery using POLYTHESE®.

- Others study safety endpoints are:
 - o Mortality rate, defined as freedom % from death
 - o Limb salvage rate, defined as freedom % from target limb amputation
 - o Adverse events, defined as any documented adverse events, including anticipated (as listed in section 6.2) and non-anticipated adverse events.

8. STATISTICAL CONSIDERATIONS

8.1. Statistical design, method and analytical procedures

All patients participating in the study who met the eligibility criteria will be included in the study population.

A descriptive analysis with clinical characteristics of all patients included in the study will be performed at the index date.

Exploratory analyses will be conducted globally and stratified by sub-populations. Sub-populations will be defined according to the three main areas of surgery:

- Thoracic
 - o Ascending aorta and/or aortic arch and/or descending thoracic aorta and/or thoraco-abdominal aorta
- Abdominal
 - o Aorto-aortic and/or aorto-iliac and/or aorto-femoral repair
- Peripheral

PROTOCOL	2021-PT-01
TITLE:	Safety and Performance of POLYTHESE® vascular prosthesis
EFFECTIVE DATE:	1 July 2021

- Peripheral artery repair and extra anatomic bypasses not crossing the knee flexion crease

Since no hypotheses will be tested, study objectives will be addressed using descriptive statistics only. Given the real-world nature of the data, the use of multiple imputation methods for missing data would introduce bias as missing data cannot be considered completely at random (MCAR) or at random (MAR). Variables will not be imputed, with the exception of dates in which the exact day is missing: the missing day will be replaced by the middle day of the month.

Continuous variables will be described with number of patients with valid / missing observations, mean and its 95% confidence interval (95%CI), standard deviation (SD), median, 25 and 75 percentiles (P25 and P75, respectively), minimum and maximum. For non-normally distributed continuous variables geometric mean and its 95%CI will be reported too.

For categorical variables counts and percentages per category will be presented. Missing observations (including invalid or outlier observations) will be tabulated as a separate category. The calculation of proportions will not include the missing/invalid category in the denominators.

P-values will be presented in the summary tables, in association with the descriptive statistics. In addition, 95% confidence intervals (95%CI) will be presented when considered convenient or relevant. Results will be graphically represented when appropriate to make interpretation easier.

The two-sided level of significance will be set at 0.05 for all the statistical tests performed.

Statistical calculations will be carried out by using R software. More details on the statistical analysis will be provided in the Statistical Analysis Plan.

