7.1. Performance endpoints

Primary performance endpoints are **primary patency rate at 1 year** after surgery using POLYTHESE®.

The others effectiveness endpoints are:

- Procedural success rate, defined as:
 - o Ability to use with no need for replacement by another device and,
 - o Effective vascular flow restoration after procedure and,
 - o In case of aneurysm, exclusion of aneurysmal portion after procedure.

PROTOCOL	2021-PT-01
TITLE:	Safety and Performance of POLYTHESE® vascular prosthesis
EFFECTIVE DATE:	1 July 2021

- Primary patency rate, defined as rate patency of the bypass graft without procedure or intervention of the conduit itself (except for occlusion)
- Primary assisted patency rate, defined as rate patency of the bypass graft with or without procedure or intervention of the conduit itself (except for occlusion) after device implantation
- Secondary patency, defined as rate patency of the bypass graft with or without procedure or intervention of the conduit itself for occlusion after device implantation
- Device Failure, defined as:
 - o Uncontrolled blood leakage from device
 - o Loss of structural integrity, e.g. rupture and/or exaggerated dilation (> 50 %)
 - o Occlusion of the device
 - o Total or partial replacement of the device required

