9.3. Data consistency

Data consistency will be verified for each variable. Harmonization of units (conversion), categorical variables consistency and ranges of numerical variables will be also verified. This step will be proceeded before database freezing and analyses. If inconsistencies are noticed, monitoring and checks will be asked from the sites.

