9.4. Missing data

Some endpoints can be missing for some subjects. Endpoints proportions will be calculated on the number of non-missing observations. No imputation method is planned.

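### Protocol section 8.1 counts outlier observations as missing and drops them from the denominators of proportions, with no exemption for values that a site has confirmed

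*Protocol*

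**What the plan says.** The rule is in the categorical-variable paragraph of Protocol section 8.1 (Statistical design, method and analytical procedures). That paragraph opens "For categorical variables counts and percentages per category will be presented" and continues "Missing observations (including invalid or outlier observations) will be tabulated as a separate category". It then fixes the denominator: "The calculation of proportions will not include the missing/invalid category in the denominators".

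Section 9.4 (Missing data) applies the same denominator to the endpoints, "Endpoints proportions will be calculated on the number of non-missing observations", and adds "No imputation method is planned". A value placed in the missing group is therefore not recovered later.

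Three other places bear on the rule:

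- The continuous-variable paragraph of section 8.1 reads "Continuous variables will be described with number of patients with valid / missing observations, mean and its 95% confidence interval (95%CI", and goes on to list the minimum and maximum. It states no exclusion of outliers.
- Section 9.3 (Data consistency) has ranges of numerical variables verified before the database is frozen: "If inconsistencies are noticed, monitoring and checks will be asked from the sites".
- Section 7.1 (Performance endpoints) gives four components of device failure. One is "Loss of structural integrity, e.g. rupture and/or exaggerated dilation (> 50" per cent).

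**The concern.** An outlier is a value that was observed and looks unusual. A missing value was not observed, and an invalid value was recorded wrongly. Section 8.1 puts all three into one category and computes proportions without it. Because outliers are named alongside invalid values, the rule reaches beyond errors. Once section 9.3 has dealt with the errors, what the word outlier adds is values that may be true.

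The study's endpoints are mostly proportions, so the categorical paragraph governs how they are reported. Outlier has no ordinary meaning for a yes/no variable. It does have one where the category comes from a number or a date, such as dilation above a threshold or an event by a given time. If a true extreme is set to missing there, and it was a failure, it leaves both numerator and denominator and the reported failure rate falls.

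This also sits badly with section 7, which aims to identify emergent risks and possible misuse, both of which can show up as unusual observations. And it leaves open, after the data are seen, whether an extreme but confirmed value counts.

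**Working it through.** **Step 1: does the text reach confirmed values?**

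- Section 8.1 classes outlier observations as missing, with no condition on verification.
- Section 9.3 asks sites to check inconsistencies, but does not say that a confirmed value is then kept.
- Section 9.4 bases endpoint proportions on non-missing observations, without imputation.

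Read together, a confirmed extreme value can still be left out. Nothing in the three sections prevents it.

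**Step 2: is there a figure in the plan to reproduce?** No. The Protocol gives no device-failure or dilation rate. The minimum of 300 subjects, 200 of them thoracic, is justified by the realistic number of operated patients and has no formula behind it.

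**Step 3: how large could the effect be?** Inputs:

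- N = 300 overall and N = 200 thoracic (section on sample size justification).
- *other* = failures of any other kind: assumed to be 6, varied to 0 and 15.
- *k* = true dilation failures set to missing: assumed to be 1, 3, 6 or 9.

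Formulas:

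- Rate with the values kept: (*other* + *k*) / N
- Rate with the values set to missing: *other* / (N − *k*)

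Results with *other* = 6:

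| *k* | N = 300, kept | N = 300, set to missing | N = 200, kept | N = 200, set to missing |
|---|---|---|---|---|
| 1 | 7/300 = 2.33% | 6/299 = 2.01% | 7/200 = 3.50% | 6/199 = 3.02% |
| 3 | 9/300 = 3.00% | 6/297 = 2.02% | 9/200 = 4.50% | 6/197 = 3.05% |
| 6 | 12/300 = 4.00% | 6/294 = 2.04% | 12/200 = 6.00% | 6/194 = 3.09% |
| 9 | 15/300 = 5.00% | 6/291 = 2.06% | 15/200 = 7.50% | 6/191 = 3.14% |

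Exact (Clopper-Pearson) 95% intervals for *k* = 3:

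- N = 300: 1.38% to 5.62% kept, 0.74% to 4.35% set to missing.
- N = 200: 2.08% to 8.37% kept, 1.13% to 6.51% set to missing.

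Varying the other failures at N = 300 and *k* = 3:

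- *other* = 0: 3/300 = 1.00% (0.21% to 2.89%) becomes 0/297 = 0% (0% to 1.23%).
- *other* = 15: 18/300 = 6.00% (3.59% to 9.32%) becomes 15/297 = 5.05% (2.85% to 8.19%).

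**Step 4: is the direction certain?** Only if the removed values are failures. If there are 9 failures in 300 and the three removed subjects are not failures, 9/300 = 3.00% becomes 9/297 = 3.03%, a small shift upwards.

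**The case against.** The strongest reply is about scope. The sentence is a tabulation rule for categorical variables. A measured diameter is continuous, and the continuous paragraph reports the minimum and maximum and excludes nothing. A recorded yes for device failure is a valid category and not an outlier. The observations are also not hidden: they are counted in their own category, after a range check and a query to the site. The denominator sentence speaks only of missing and invalid data, which could be read as whatever remains unusable after that check.

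Part of this stands. A reader might infer that the rule deletes the graft dilation that defines device failure. The Protocol does not support that:

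- It nowhere classes a dilation value as an outlier, and nowhere says that outliers are removed before failure is derived.
- Dilation is one example within one of four failure components.
- Failures can also be captured without any numerical filter. Section 9.2 collects failure modes and documented adverse events, and section 6.2 lists graft dilatation as an anticipated event.
- Section 9.2 names no follow-up diameter variable. Its only diameter is in the identification data of the implanted prosthesis.

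A reader might also infer a bias in the primary endpoints, patency at 1 year and mortality at 30 days. These are event-status endpoints, and no effect on them is shown here.

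The missing definition of an outlier is not counted as a fault, since it may be in the SAP, which is not available.

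What the reply does not remove is the stated rule. Section 8.1 puts outliers inside the category that leaves the denominator, and no text exempts a confirmed value. A definition in the SAP would settle which observed values are treated as missing, but they would still be treated as missing. Counting them in a missing category does not put them back into the reported rate.

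**Conclusion.** The point holds as a badly fixed rule: section 8.1 treats observed outliers as missing and leaves them out of proportions, confirmed or not. For categories derived from measurements or dates, true extremes can be lost. Understated device failure is a possible consequence, and it requires the rule to be applied to a measured dilation before failure is derived.

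The size is unknown. The figures above rest on assumed counts and on every one of the *k* dilations being set to missing. With 6 other failures in 300, the loss runs from 2.33 − 2.01 = 0.32 percentage points for one dilation to 5.00 − 2.06 = 2.94 points for nine. A fall to zero needs the further assumption that there are no other failures.

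This is a minor point, worth correcting because the correction is so small.

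**What to change.** - In section 8.1, delete the words *or outlier* from the sentence on missing observations.
- Add that a value is set to missing only when the section 9.3 check finds it erroneous and it cannot be corrected.
- State that verified extreme values stay in both numerator and denominator.
- List, by endpoint, the values set to missing and the reason.

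The cost is a change to one sentence, a short addition and one listing. True errors remain covered by the word *invalid*, so no useful protection is lost.

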8.1. Sample size justification

Data from a minimum of 300 subjects will be evaluated. A minimum of 200 subjects will be evaluated for thoracic location of surgery. The number of patients has been chosen in accordance with the realistic number of operated patients in the involved hospitals.

9. DATA MANAGEMENT

9.1. Data sources

Real World Data sources used to generate Real World Evidence are:

- Data derived from Electronic health Record
- Medical claims and/or billing data
- Product and/or disease registry data

PROTOCOL	2021-PT-01
TITLE:	Safety and Performance of POLYTHESE® vascular prosthesis
EFFECTIVE DATE:	1 July 2021

9.2. Data to collect

As mentioned previously considering study is retrospective and considering that every site can have different ways to follow their patients after surgery, data will be collected as much as possible in order to determine the clinical safety and performance.

The following data will be collected, when available according to participating site available data.

- **Identification and demographic data**

- Patient identification
- Indication and location of the treatment
- Location of the surgery
- Patients demographics
 - Year of birth
 - Sex
 - Mass
- Identification of implanting physician
- Name of the institution

- **Pre-operative data**

- Risks factors, such as hypertension, diabetes, coronary artery disease, hyperlipidaemia, tobacco use, obesity, anaesthesia risk and any cardiovascular risk factor.
- Summary of previous vascular interventions at the same or other relevant vascular sites, including non-surgical interventions and previously implanted vascular devices (e.g. stents, endovascular prostheses, surgically placed vascular grafts)
- Relevant medications
- Diagnostic criteria
 - Clinical assessment (e.g. non-invasive hemodynamic assessment);
 - Objective assessment (e.g. C.T. scanning, magnetic resonance imaging, ultrasonography, arteriography, duplex Doppler)

- **Operative data**

- Date of procedure
- Identification data for the vascular prosthesis including configuration (e.g. straight uniform or bifurcated) and diameter
- Information regarding the procedure:
 - Identity of native vessel treated

PROTOCOL	2021-PT-01
TITLE:	Safety and Performance of POLYTHESE® vascular prosthesis
EFFECTIVE DATE:	1 July 2021

- Details of anastomoses (e.g. type (end-to-end), location)
- Length of prosthesis implanted (if available)
- Adjunctive vascular procedures
- Relevant medication (e.g. heparin, other anticoagulants)
- Assessment of prosthesis function and mode of assessment if available (e.g. intraoperative angiography, intraoperative Doppler)
- Failure modes and adverse operative events
- **Post-operative data**
 - Interval of follow-up (e.g. discharge or 7 d to 14 d after surgery, 30 days, 6 and 12 months after surgery, up to 5 years for exploratory time points)
 - Date of follow-up visits
 - Summary of vascular interventions, including minimally invasive procedures
 - Clinical evaluation:
 - Clinical assessment (e.g. non-invasive hemodynamic assessment)
 - Objective assessment of prosthesis (e.g. C.T. scanning, magnetic resonance imaging, ultrasonography, arteriography, duplex Doppler)
 - Relevant medications (e.g. anticoagulants or antiplatelets)
 - Any documented adverse events including the events listed in section 6.2 anticipated risks and any events that lead to the patient's death
- **Any documented adverse events data**

As far as available the following data will be collected per adverse event:

 - Type of event, date of occurrence, severity, management (e.g. none, medical treatment, endovascular procedure, open surgery), outcome (e.g. continuing, resolved, unknown, death)
 - Any Documentation of prosthesis involvement
 - Any Documentation of probable causative factors (e.g. caused by the prosthesis, patient factors, technical factors)
 - Explant data:
 - Date
 - Whether the subject is living or deceased
 - Reason for explant, if applicable

PROTOCOL	2021-PT-01
TITLE:	Safety and Performance of POLYTHESE® vascular prosthesis
EFFECTIVE DATE:	1 July 2021

- Relevant observations (e.g. device integrity, device positioning, tissue incorporation, vascular tissue erosion), if available

A separate document with all available data to collect will be produced in a second time to add further details depending on the level of details available.

9.3. Data consistency

Data consistency will be verified for each variable. Harmonization of units (conversion), categorical variables consistency and ranges of numerical variables will be also verified. This step will be proceeded before database freezing and analyses. If inconsistencies are noticed, monitoring and checks will be asked from the sites.

9.4. Missing data

Some endpoints can be missing for some subjects. Endpoints proportions will be calculated on the number of non-missing observations. No imputation method is planned.

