Safety secondary endpoints	
 • Mortality rate during procedure or at discharge, at 6 months and 1 year after surgery using POLYTHESE® • Limb salvage rate at 30 days, 6 months and 1 year after surgery using POLYTHESE® • Adverse event during procedure or at discharge, at 30 days, 6 months and 1 year after surgery using POLYTHESE®
Exploratory endpoints	
 • After 1 year until the end of follow-up (5 years) using POLYTHESE®: 
 ○ Primary patency ○ Primary assisted patency ○ Secondary patency ○ Device failure ○ Mortality ○ Limb salvage ○ Adverse events ○ Identify possible systematic misuse or off-label use of POLYTHESE®, with a view to verifying that the intended clinical purpose is correct.
Inclusion criteria	Subjects who did receive POLYTHESE® (IC, ICT, IC-3GL) at least one year ago for replacement or bypass of arteries presenting aneurysm or arterial disease
Exclusion criteria	Patients who have objected to the collect of their data
Duration of the data collect:	6 months from first site operational to collect data until data delivery
Data to be collected (as far as available)	
 • Identification and demographic data 
 ○ Patient characteristics ○ Indication and location of surgery ○ Patients demographics and risk factors ○ Summary of previous cardiovascular interventions ○ Relevant medications ○ Diagnosis • Operative data 
 ○ Date of procedure

PROTOCOL	2021-PT-01
TITLE:	Safety and Performance of POLYTHESE® vascular prosthesis
EFFECTIVE DATE:	1 July 2021

- Identification data for the prosthesis
- Information related to the surgical procedure
- Relevant medication
- Assessment of prosthesis function and mode of assessment if available
- Device failure modes and documented adverse operative events

- **Post-operative data (follow-up)**

- Date of follow-up visits
- Summary of vascular interventions, including minimally invasive procedures
- Clinical evaluation
- Relevant medications
- Device failure modes and documented adverse events

- **Any documented adverse events data (as far as available)**

- Type of event, date of occurrence, severity, management, outcome
- Any Documentation of probable causative factors (e.g. caused by the prosthesis, patient factors, technical factors)

Timepoints of collected data	- During procedure and at discharge (7-14 days)

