	- 30-days after surgery ('peri-operative')
	- 6, 12 months
	- Annually up to 5 years post procedure

3. INTRODUCTION.

POLYTHESE® IC and ICT devices are CE-marked and were initially introduced in the international market in 1997, followed in 2003 and 2005 respectively by POLYTHESE® and POLYTHESE® devices. POLYTHESE® IC-3GL devices were then introduced in 2009.

Since January 2002, more than 60 000 single devices have been sold across various markets worldwide.

PROTOCOL	2021-PT-01
TITLE:	Safety and Performance of POLYTHESE® vascular prosthesis
EFFECTIVE DATE:	1 July 2021

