5.3. Subjects

The participating hospitals will screen all potential subjects and will select those who are appropriate for study inclusion, i.e. subjects implanted with POLYTHESE® for at least one year, or with complete data to death. As the study explores real world data, there is no exclusion criteria for subjects and all subjects with POLYTHESE® implanted for at least one year and have not objected to the collect of their data will be included in the study.

All data will be retrieved from medical charts for each patient from time of surgery (considered as index date) until a maximum of 5 years after surgery.

Data from a minimum of 300 from 3 to 8 different sites in France will be evaluated. A minimum of 200 subjects with thoracic location of surgery will be evaluated.

Not more than 50% of study total enrolled subjects shall pertain to one unique centre.

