5.3.1. Inclusion criteria

Patients must meet the following inclusion criteria in order to be eligible for inclusion in the study:

- Patient has a minimum of 1-year post-operative follow-up data available, or complete data to death

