7. OBJECTIVES AND ENDPOINTS

The principal objective of the POLYTHESE® study is to describe safety and performance of POLYTHESE®. Identification and analysis of potential emergent risks will be performed according to the availability of the collected adverse events.

Identification of possible systematic misuse or off-label use of POLYTHESE®, with a view to verifying that the intended purpose is correct, will also be performed according to the availability of the data.

The following table summarizes the performance and safety endpoints and timeframe after surgery.

Study endpoints	At surgery	Time period following surgery			
		30 days	6 months	1 year	>1 year until 5 years of follow-up
Performance endpoints					
Primary patency rate*	---	X	X	X*	X
Primary assisted patency rate	---	X	X	X	X
Secondary patency rate	---	X	X	X	X
Device Failure	X	X	X	X	X
Procedural success rate	X	---	---	---	---
Safety endpoints					
Mortality rate*	X	X*	X	X	X
Limb salvage rate	---	X	X	X	X
Adverse events **	X	X	X	X	X

* Primary endpoint

** Listed in section 6.2

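### After year 1, proportions on non-missing observations bias event rates up or down, depending on the denominator, because follow-up varies from 1 to 5 years

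*Protocol*

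**What the plan says.** Section 9.4 states: "Endpoints proportions will be calculated on the number of non-missing observations. No imputation method is planned". Section 8.1 (Statistical design, method and analytical procedures) says the same for categorical variables: "The calculation of proportions will not include the missing/invalid category in the denominators". It limits the analysis to descriptive statistics and leaves further detail to the SAP. The protocol names no censoring, person-time or time-to-event method.

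Follow-up is variable by design. A patient enters under this criterion in 5.3.1: "Patient has a minimum of 1-year post-operative follow-up data available, or complete data to death". Charts are read "until a maximum of 5 years after surgery" (5.3), and the synopsis lists late time points as "Annually up to 5 years post procedure". Section 9.2 collects data where available and accepts that sites follow patients differently.

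Patency, device failure, mortality, limb salvage and adverse events after 1 year are exploratory endpoints. The synopsis describes the period as "After 1 year until the end of follow-up (5 years) using POLYTHESE", and the table in section 7 gives it a single column, ">1 year until 5 years of follow-up". Section 7.2 has "Mortality rate, defined as freedom % from death", without an estimator or denominator.

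**The concern.** Up to 1 year the entry criterion protects the rule, since every included patient has a year of data or is known to have died. After 1 year that protection ends. An event, once recorded, settles the patient's status at all later times. Freedom from the event has to be observed for as long as the time point requires. Dropping patients with unknown status therefore removes only event-free patients and inflates the event rate. If a patient with no recorded event is instead treated as a non-missing non-event, the rate is deflated. Reporting the whole period after 1 year as one window leaves the same choice open.

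At stake is the long-term description of the device. Section 5.2 names long-term assessment, with thoracic use, as where the evidence is thin, and the synopsis objective covers the expected lifetime of the device. Missing counts will be tabulated, so a reader would see the gap, but the percentage beside them would remain uncorrected.

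**Working it through.** The protocol states no event rate or precision figure here, and 300 patients (200 thoracic) is a feasibility number, so there is no figure of the plan to reproduce.

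**From the protocol:** follow-up of 1 to 5 years, the non-missing denominator, at least 300 patients. **Assumed:** constant annual death hazard h; time from implant to data collection, A, spread evenly from 1 to L years with L = 10 or 20, independent of outcome; charts complete; t = 5 years.

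**Formulas**
- Truth: 1 − exp(−5h)
- Events seen by year 5: E = [4 − (exp(−h) − exp(−5h))/h + (L − 5)(1 − exp(−5h))]/(L − 1)
- Known event-free at year 5: S = (L − 5)/(L − 1) × exp(−5h)
- Known-status proportion: E/(E + S). All-patient proportion: E.

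**Worked case**, h = 0.05, L = 10: truth = 1 − 0.7788 = 22.1%. E = [4 − 3.4486 + 5 × 0.2212]/9 = 0.1842. S = (5/9) × 0.7788 = 0.4327. Known status: 0.1842/0.6169 = 29.9%. All patients: 18.4%.

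| Death per year | Truth, 5 years | L = 10: known status | L = 10: all patients | L = 20: known status | L = 20: all patients |
|---|---|---|---|---|---|
| 3% | 13.9% | 19.4% | 11.5% | 15.8% | 12.8% |
| 5% | 22.1% | 29.9% | 18.4% | 24.9% | 20.4% |
| 8% | 33.0% | 42.6% | 27.6% | 36.5% | 30.4% |

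**One pooled window, after year 1 to year 5**, among 1-year survivors at 5% per year. The same argument applies with time counted from year 1 and truth 1 − exp(−4h) = 18.1%. Result: 23.8% or 14.2% (L = 10), 20.1% or 16.3% (L = 20).

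**All implanted at least 5 years ago, but charts end at rate c per year after year 1.** E = 1 − exp(−h) + exp(−h) × h/(h + c) × [1 − exp(−4(h + c))], and S = exp(−5h − 4c). At h = 5%: c = 5% gives 0.2056/(0.2056 + 0.6376) = 24.4% known status, or 20.6% all patients. c = 20% gives 0.1690/(0.1690 + 0.3499) = 32.6%, or 16.9%.

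**Follow-up actually ending at 1, 2, 3, 4 or 5 years in equal shares**, h = 5%: E = 0.1371 and S = 0.2 × 0.7788 = 0.1558, giving 46.8% or 13.7%. Shares of 40/25/15/10/10% give 57.3% or 10.4%; shares of 10/10/15/25/40% give 35.2% or 16.9%.

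**Device failure** at q = 2% per year with death at h = 5%. Truth = q/(q + h) × [1 − exp(−5(q + h))] = 8.4%. For L = 10, with the same averaging over A, failures seen are 0.0706, deaths without failure 0.0706 × h/q = 0.1765, and known event-free (5/9) × exp(−0.35) = 0.3915. Known status: 0.0706/0.6386 = 11.1%. If deaths are dropped as missing: 0.0706/0.4621 = 15.3%. All patients: 7.1%. For L = 20: 9.4%, 12.3% and 7.8%.

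**Does Kaplan-Meier recover the truth?** In 4,000 simulated studies of 300 patients per window at 5% mortality, the mean 5-year estimate was 22.2% (SD 2.8 points, about 129 at risk) for L = 10 and 22.1% (SD 2.6, about 184 at risk) for L = 20, with interval coverage of about 94%. A crude proportion limited to patients whose potential follow-up reaches 5 years, whatever their outcome, gave 22.2% (SD 3.3) and 22.1% (SD 2.8): also unbiased, but less precise.

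**Against sampling error.** The 95% half-width is 1.96 × 2.8 = 5.5 points for L = 10 and 1.96 × 2.6 = 5.1 for L = 20. At 5% mortality the known-status error is +7.7 points for L = 10 (29.86 − 22.12) and exceeds it. The other three, +2.8, −3.7 and −1.7, do not.

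**The case against.** The strongest reply is that section 9.4 says how proportions are computed, not that every late endpoint must be reported as a crude proportion. Kaplan-Meier is descriptive, fits the freedom-from-event wording of 7.2, and could be set in the SAP. That is fair as to intent. But the rule is stated twice, for endpoints in general, with no exception for late time points; a SAP using survival estimates would depart from it. This is a rule fixed badly rather than a detail left open.

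A second reply is that the downward error contradicts 9.4, because patients not followed to t should be dropped. At a strict annual time point that is the literal reading, and the upward error is then the one to expect. The downward error stays possible because a chart with no recorded event may be read as a non-missing non-event, and because the section 7 table allows one pooled window.

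Other limits stand. All affected endpoints are exploratory and neither primary endpoint is touched. The sizes rest on assumed hazards and windows. If patency is counted only among patients imaged at a visit, the direction of error is not established. Kaplan-Meier needs independent censoring, which section 8.1 itself puts in doubt by calling the missing data neither MCAR nor MAR. The entry criterion also admits early deaths while excluding survivors with under a year of data. In one simulation (10% first-month deaths, 5% per year afterwards, 10 to 20% per year chart loss, all assumed) Kaplan-Meier still overstated 5-year death by about 0.8 to 1.7 points. That is a separate, modest problem and does not cancel the gain.

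**Conclusion.** The concern holds and should be fixed. With follow-up varying from 1 to 5 years, the stated denominator rule gives biased event rates after year 1: too high on known status, too low if patients not followed to t are kept as event-free. At 5% annual mortality and implants 1 to 20 or 1 to 10 years old, the 5-year error is about +3 to +8 points or −2 to −4 points on a true 22.1%; it is larger if observed follow-up is mostly short. These sizes assume constant hazards and follow-up unrelated to outcome. The bias vanishes if every patient has documented status to t. It would also be absent, with complete charts, under a denominator limited to patients whose potential follow-up reaches t, but the protocol does not specify one. Rates up to 1 year are not affected by the variable follow-up.

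**What to change.** In sections 9.4 and 8.1, for endpoints after 1 year:

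- Replace the non-missing proportion for mortality with Kaplan-Meier estimates from surgery at each annual time point, censored at the last date on which status is documented, with numbers at risk and 95% confidence intervals.
- For patency loss, device failure and amputation, use cumulative incidence with death as a competing event.
- State that patency loss is dated at the assessment that detects it.

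The cost is protocol and SAP wording and standard R code. Procedure, visit and event dates are already to be collected where available, so no new data item is needed. Late intervals will be wide. The change removes the bias from staggered follow-up; it does not cure informative loss to follow-up, and it does not fully handle patency loss that is seen, and therefore dated, late.
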